5.5.4 Subject withdrawal

The criteria for terminating participation in the study are detailed below:

1. Serious adverse event that is study-related (see definition further below), as recommended by the Investigator, patients with grade 3 or 4 adverse events following their initial treatment who have evidence of treatable prostate cancer on month 3 biopsy will not undergo re-treatment, will be withdrawn from the study and proceed with standard of care unless justification for continuing on study is specifically sought and approved from the IRB.
2. Subject withdrawal: at any time, a subject can withdraw from the study at his request or on the basis of the Investigator's clinical judgment.
3. Patients with evidence of clinical deterioration on the same side such as Gleason grade 5 cancer, more than 2 sextants including Gleason grade 4 cancer on the treated side on the 3-month re-biopsy will be withdrawn from the study and proceed with standard care.
4. Major protocol violation, defined as any violation that may impact the safety of a study subject.
5. Termination of the study by the Sponsor.

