5.5.6 Replacement of premature withdrawals from trial

The Sponsor reserves the right to replace a subject who is removed or withdraws from the study before the month 3 biopsy with a new subject. A subject who is removed or withdraws after the month 3 biopsy will not be replaced.

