7 OUTCOMES ASCERTAINMENT

7.1 Prostate biopsy

All subjects will undergo biopsy at 3 and 12 months according to protocol. The need for subsequent biopsy beyond 12 months will be at the discretion of the investigator according to standard of care. All biopsy procedures will consist of a transrectal ultrasound guided prostate biopsy with a minimum of 12 cores and include both lobes of the prostate gland. Any suspicious volumes meeting PIRADS (version 2) criteria of level 4 or 5 found on MRI will be targeted with at least 2 cores taken from each suspicious lesion. Patients will undergo pre-biopsy preparation using standard of care practices for the institution that should include the use of peri-procedural antibiotics. Patients who fail to receive antibiotics for the biopsy procedure will be considered a violation.

Anatomopathological reports will include:

1. The number and length of cores taken,

2. The number and the location of cores with cancer,
3. The cancer core length (CCL) which is linear millimeters of cancer on each core and the percentage of cancer on each core,
4. The Gleason grading of each core.

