##### ***Efficacy population***

The efficacy population will include patients who complied with the protocol for inclusion criteria and exclusion and follow-up received the appropriate dose of TOOKAD® Soluble, LDI and energy delivered and underwent the VTP procedure, receiving the ascribed dose of TOOKAD® Soluble and light, had no major protocol deviations and provided data at the 12 month biopsy. A "major" protocol deviation is defined as one which, in the opinion of the PI, could importantly influence the result of the 12 months biopsy and which is adjudicated before the 12-month biopsy.

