**IPSS questionnaire**

Scores with at least 1 but not more than 50% missing items will be imputed using the formula:  $S = s \times T \div t$  where s is the observed score, S is the imputed score, T is the maximum total score for the IPSS and t is the maximum score possible from the completed questions. Missing total scores will be imputed using a multiple imputation method (Markov Chain Monte Carlo method).

Other missing data, including biopsy data, will not be replaced.

A subject with missing Month 12 biopsy will be counted as failure for the primary analysis.

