***Efficacy analysis***

All analyses will include the “efficacy population” as described above with a secondary analysis including patients undergoing retreatment at 3 months.

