### **Primary efficacy analysis**

The proportion of patients with no pattern 4 or 5 found in the 12 month biopsy will be reported along with a one-sided 90% confidence interval. Patients who have pattern 4 or 5 found before 12 months and who receive radical therapy will be treated as treatment failures. The treatment will be considered a success if the lower bound, rounded to 0.01, is 70% or higher. For a sample size of 44, this means that treatment will be declared a success if 35 or more patients respond.

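### The SAP both excludes men without a 12-month biopsy and counts them as failures in the primary analysis, and does not say which rule governs

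*SAP*

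**What the plan says.** Five pieces of text bear on who is in the primary denominator.

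- **SAP, Efficacy population.** Members must meet the eligibility, follow-up, dose, LDI and energy requirements, and must be men who "had no major protocol deviations and provided data at the 12 month biopsy".
- **SAP, Efficacy analysis.** All analyses use the efficacy population "as described above with a secondary analysis including patients undergoing retreatment at 3 months".
- **SAP, Handling of missing data (end of the IPSS paragraph).** "A subject with missing Month 12 biopsy will be counted as failure for the primary analysis".
- **SAP, Primary efficacy analysis.** "Patients who have pattern 4 or 5 found before 12 months and who receive radical therapy will be treated as treatment failures". Success requires a one-sided 90% lower bound that, rounded to 0.01, reaches 70%. The worked example is: "For a sample size of 44, this means that treatment will be declared a success if 35 or more patients respond". Neither the denominator nor the interval method is named.
- **Protocol 10.3.** It names no population for the primary endpoint and gives no rule for a missing biopsy. The intention-to-treat set in Protocol 10.2.2.4 is tied to descriptive statistics.

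The SAP section on changes from the protocol has no text that settles the matter. The synopsis plans 50 men in order to obtain at least 44 evaluable.

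**The concern.** Read literally, the population definition removes every man the missing-biopsy rule was written for. It also removes any man covered by the early-failure rule who has no 12-month biopsy. The follow-up clause adds a second route out: Protocol 7.1 states "All subjects will undergo biopsy at 3 and 12 months according to protocol", so a missed biopsy can also be read as non-compliance with follow-up.

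Missingness need not be unrelated to outcome. Under Protocol 5.5.4, men with defined deterioration "on the treated side on the 3-month re-biopsy will be withdrawn from the study and proceed with standard care"; the synopsis and Protocol 4.1 contain similar withdrawal provisions. Protocol 6.4.11 lets men choose radical therapy at any time. Protocol 5.5.6 adds: "A subject who is removed or withdraws after the month 3 biopsy will not be replaced". If the men who drop out this way include more failures than the rest, excluding them raises the reported success rate.

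This is a single-arm trial with one pass/fail threshold. Two analysts who each follow the SAP could use different denominators and report opposite primary conclusions.

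**Working it through.** **Inputs.** Null rate 0.70, one-sided alpha 0.10, assumed rate 0.836, n = 44 (SAP, Planned sample size). Pass rule and cut-off of 35 (SAP, Primary efficacy analysis). 50 included for 44 evaluable (Protocol synopsis). The interval method is not given, so three are shown.

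**1. The plan's own figures reproduce.** Normal approximation: n = [(1.2816·√(0.70·0.30) + 0.8416·√(0.836·0.164)) / 0.136]² = 43.7, so 44. For n = 44, exact, Wilson and Wald bounds all give 35 as the smallest passing count (34/44 gives 0.672, 0.683 and 0.692, none reaching 0.70).

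**2. Add missing men as failures to 35 responders among 44 biopsied men.** One-sided 90% lower bounds:

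| Result | Exact | Wilson | Wald | Verdict after rounding |
|---|---|---|---|---|
| 35/44 | 0.6964 | 0.7076 | 0.7175 | passes on all three |
| 35/45 | 0.6784 | 0.6894 | 0.6984 | passes on Wald only |
| 35/46 | 0.6615 | 0.6722 | 0.6803 | fails on all three |
| 35/50 | 0.6018 | 0.6117 | 0.6169 | fails on all three |

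**3. Pass marks c(n) from the same rule.**

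| n | 44 | 45 | 46 | 47 | 48 | 49 | 50 |
|---|---|---|---|---|---|---|---|
| Exact | 35 | 36 | 37 | 38 | 38 | 39 | 40 |
| Wilson | 35 | 36 | 36 | 37 | 38 | 39 | 39 |
| Wald | 35 | 35 | 36 | 37 | 38 | 38 | 39 |

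**4. How often the two readings disagree.** Assume 50 men, all otherwise eligible, m without a biopsy, and responders X ~ Bin(50−m, 0.836). Exclusion passes if X ≥ c(50−m); missing-as-failure passes if X ≥ c(50). Disagreement is P(X ≥ c(50−m)) − P(X ≥ c(50)).

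| m | Exact | Wilson |
|---|---|---|
| 1 | 0.831 − 0.724 = 0.107 | 0.831 − 0.831 = 0.000 |
| 2 | 0.847 − 0.613 = 0.235 | 0.847 − 0.746 = 0.102 |
| 3 | 0.767 − 0.485 = 0.282 | 0.863 − 0.637 = 0.226 |
| 6 | 0.826 − 0.131 = 0.695 | 0.826 − 0.250 = 0.576 |

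Wald gives 0.074 at m = 1 and matches Wilson at m = 2, 3 and 6.

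**5. False success under exclusion (assumption-based range).** Let the overall rate be 0.70 in 50 men (35 responders expected), with a share s of the m missing men being failures. The rate among biopsied men is p = (35 − m(1−s)) / (50−m).

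- m = 2, cut-off 38/48: s = 0.30 gives p = 0.700 and risk 0.107; s = 0.50 gives 0.132; s = 1 gives p = 35/48 = 0.729 and risk 0.211.
- m = 6, cut-off 35/44: s = 0.30 gives 0.109; s = 0.50 gives 0.201; s = 1 gives p = 35/44 = 0.795 and risk 0.588.

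Here s = 0.30 means missing at random. The documents give neither m nor s.

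**The case against.** The strongest reply is that the readings are not equally plausible. The missing-biopsy sentence is specific to the primary analysis and the population sentence is general. Letting the specific rule prevail keeps every sentence working and gives one answer: missing means failure. The early-failure rule points the same way. On this view the biopsy condition is a drafting leftover. That may well be what was meant, but the Efficacy analysis section says all analyses and the biopsy is a condition of membership, so the text does not decide it. If it is what was meant, the fix writes it down.

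On size, exactly 35 of 44 has probability only 11.5% at 83.6%. The most likely count is 37, and 37/46 still passes (0.709, 0.719 and 0.729). That is fair, and step 4 is therefore the better measure than the boundary example. The six-missing figures require all six surplus men to lack only the biopsy. Some could be non-evaluable on dose, LDI or eligibility, which both readings exclude. Those figures are an extreme case.

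The pass rule does apply to any n, with 44 as its example; what is missing is the interval method. The sample size also rests on evaluable men (Protocol 10.1), which lends some support to a biopsied set. Two related points stand: Protocol 10.2.2.5 drops men given radical therapy from the per-protocol set, which the SAP's efficacy population closely resembles, and the retreatment phrase in the Efficacy analysis section leaves it unclear whether retreated men are in the main analysis. If they are not, n could fall below 44.

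**Conclusion.** The concern holds. The two rules cannot both operate, and nothing in either document ranks them. Under the exact bound the choice changes the primary verdict in about 11%, 23% and 28% of trials with one, two and three missing biopsies; under Wilson in about 0%, 10% and 23%. These figures assume an 83.6% response among biopsied men and 50 men who differ only in having the biopsy. Six missing gives 69% or 58% as the upper extreme.

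The direction of bias from exclusion is upward if men without a biopsy fail more often than the rest. Its size is unknown; the false-success range of 11% to 21% with two missing only illustrates what it could be. This must be settled before the primary analysis, because the denominator decides the result.

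**What to change.** For the primary analysis:

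1. Remove the 12-month-biopsy condition from the efficacy population, and state that a missed biopsy is not in itself non-compliance with follow-up or a major deviation. The eligibility, dose, LDI, energy and other deviation criteria may stay.
2. State that the missing-biopsy and early-failure rules apply to every man in that set, that the radical-therapy exclusion in Protocol 10.2.2.5 does not remove men from it, and whether retreated men are included.
3. Name the interval method and tabulate the pass mark for each n from 44 to 50 as in step 3, with the general rule covering any other n.
4. Keep the biopsied-only set as a supportive analysis, and report the number of missing Month 12 biopsies with reasons. An analysis of all VTP-treated men can be added as a sensitivity analysis.

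The work is SAP wording and a short table, with no new data. The real cost is power, because the 83.6% came from men with biopsies available (Protocol 10.1). With n = 50, each man missing at random with probability f and missing counted as failure, the success probability per man is 0.836(1−f):

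| f | Power, cut-off 40 (exact) | Power, cut-off 39 (Wilson or Wald) |
|---|---|---|
| 0 | 81% | 89% |
| 6% | 48% | 62% |
| 10% | 27% | 40% |
| 12% | 19% | 30% |

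This loss is already present if the missing-biopsy rule is the one intended.

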- Patients' reported outcome measures (PROMs) impairment: urinary symptoms using IPSS and erectile functions using IIEF prior to treatment beginning and then 1, 3, 6, 12, 24, 36, 48 and 60 months after completing treatment
- Severe prostate cancer-related events: cancer extension to T3, metastasis or prostate cancer-related death
- Use of secondary prostate cancer treatment following VTP will include surgical removal of the prostate gland, radiation treatment to the prostate gland, use of hormone or chemotherapies.
- Adverse events
- Serum PSA measurements in ng/mL.

SAMPLE SIZE JUSTIFICATION

A proportion of responders of $r=70\%$ at 12 months is considered to be a clinically significant expectation in localized intermediate-risk prostate cancer patients.

Based on historical data in similar series of patients, a minimum of $N=44$ patients is required to test the null hypothesis $H_0: "r \leq 70\%"$ vs. $H_1: "r > 70\%"$, with 80% power and 5% as alpha risk.

MANUFACTURING INVESTIGATIONAL PRODUCT:

TOOKAD® Soluble is manufactured by Praxis Pharmaceutical S.A, Vitoria-Gasteiz, Spain.

TOOKAD® Soluble batches are released by Steba Laboratories, Ness Zion, Israel.

Laser equipment: Intermedic Arfran S.A, Spain

FLOW CHART: Schedule of Events

Procedure	V1 and screening period	V2 VTP	V3 Day 7+/- 2 days	V4 Month 1 +/- 1 wk	V5 Month 3 +/- 2 wks	V6 Month 6 +/- 2 mos	V7 Month 12 +/- 2 mos	V8-11 Annual f/u +/- 3 mos
Informed Consent	X							
Inclusion/exclusion Criteria	X							
Medical History	X							
TNM Staging	X							
VTP Treatment		X						
Clinical Examination	X	X ^a						
Prostate Biopsy	X ^b ≤6mos before consent				X ^c		X	X ^d
Digital Rectal Examination	X							
Prostate Specific Antigen	X ^e	X		X	X	X	X	X
Standard Hematologic Tests	X ^e	X ^a		X	X	X	X	X
Standard Blood Chemistry Tests	X ^e	X ^a		X	X	X	X	X
Standard Blood Coagulation Tests	X ^e							
Additional Inclusion Blood Tests	X ^e							
Prostate Volume	X	X						
MRI	X ^d				X		X	X ^d
Patient-Reported Outcome Measures (PROMs)	X			X	X	X	X	X
Study Medication		X						
Concomitant Medications	X	X ^a	X	X	X	X	X	X
Adverse Events		X ^a	X	X	X	X	X	X

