6.4.7 Visit 7 (V7): Month 12 (±2 months)

The procedures for this visit are:

1. Blood collection for laboratory and PSA testing
2. Recording of AEs
3. Assessment of concomitant medication
4. Collection of IPSS and IIEF questionnaires
5. Performance of prostate biopsy

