6.4.11 Post-procedure or follow-up assessments

Based on the results of post-procedure or follow-up assessments, or upon decision by them or their clinician, patients may at any time decide to undergo additional radical therapy.

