#### **Time to additional radical therapy (Days)**

The time to additional radical therapy will be calculated from the date of treatment to the date of initiation of the first radical therapy. If a subject did not receive any additional radical therapy during the study then the time to additional radical therapy for this subject will be censored at the study termination date.

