### **Secondary efficacy analysis**

#### **Biopsy results**

Biopsy results at each follow-up (3, 12, 24, 36, 48 and 60) for each definition of positive biopsy will be given as cumulative frequency, along with 95% C.I., with radical therapy as a competing risk. The alternative definitions of positive biopsy are:

1. Presence of any pattern 4 or 5 disease (primary endpoint)
2. Presence of cancer of any grade
3. Presence of any pattern 4 or 5 disease in the treated lobe
4. Presence of cancer of any grade in the treated lobe

Analyses will be repeated with radical treatment counted as an event. As retreatment at 3 months is allowed, 3 month results will be treated as a binary endpoint with 95% C.I. presented in a table.

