#### **Initiation of additional therapy**

Additional prostate cancer treatment is defined as any treatment for prostate cancer other than TOOKAD® Soluble-VTP, including surgery, radiotherapy (external beam, brachytherapy, focused), high intensity focused ultrasound, cryotherapy, hormonal therapy for cancer, chemotherapy for cancer.

The time to initiation of therapy will be analyzed using Kaplan-Meier estimates, presented as a survival curve with corresponding 95% confidence intervals. Subjects who did not initiate any therapy will be censored at the time of study termination. The corresponding Kaplan-Meier curve will also be presented. As a sensitivity analysis, this analysis will be repeated excluding ablative therapies and hormonal therapy, that is, an analysis of time to radical therapy (surgery, radiotherapy). Tables and figures will be provided as appropriate.

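### The SAP efficacy population requires 12-month biopsy data, so the month-3, cumulative-incidence and time-to-therapy results generally leave out men with early surgery or withdrawal

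*SAP*

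**What the plan says.** **Population.** SAP, Efficacy population, requires compliance with eligibility and follow-up, the planned drug and light dose, and that the man "had no major protocol deviations and provided data at the 12 month biopsy". SAP, Efficacy analysis, applies this set to all efficacy analyses, "as described above with a secondary analysis including patients undergoing retreatment at 3 months". No other efficacy set is defined.

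**Outputs under that heading.** In SAP, Biopsy results, positive biopsies are given as cumulative frequency with radical therapy as a competing risk, then again with radical therapy as an event. For month 3, "3 month results will be treated as a binary endpoint with 95% C.I. presented in a table". In SAP, Initiation of additional therapy, "The time to initiation of therapy will be analyzed using Kaplan-Meier estimates". Neither section names a population. The start date is given only for the narrower radical-therapy variable: "The time to additional radical therapy will be calculated from the date of treatment to the date of initiation of the first radical therapy".

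**How men leave before month 12.** In the protocol synopsis, "Use of secondary prostate cancer treatment following VTP will include surgical removal of the prostate gland". In protocol 6.4.11, "patients may at any time decide to undergo additional radical therapy". Protocol 4.1 and 5.5.4 withdraw certain men after the month-3 biopsy. The primary biopsy visit is "Visit 7 (V7): Month 12 (±2 months").

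**Protocol populations.** Section 10.2.2.4 plans descriptive statistics on the intention-to-treat set and also on the per-protocol set. Section 10.2.2.5 keeps men with additional surgery, radiation, hormone therapy or chemotherapy in the former and removes them from the latter. The SAP has no intention-to-treat display, and nothing appears under its heading for changes from the protocol analysis.

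**The concern.** Time to additional therapy and month-3 biopsy status are both counted from treatment. Requiring a 12-month biopsy for membership makes them conditional on a later event, and that event depends on outcome: a man who did badly early is more likely to have had surgery or to have been withdrawn, and so to have no 12-month biopsy.

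At stake is secondary objective 9, the use of other prostate cancer therapies after VTP, and probably the month-3 positivity rate. Both would tend to look better than they are among all treated men. The planned subject listings and the table of discontinuations with reasons would still show these men, but would not return them to the estimates.

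**Working it through.** **1. Which set applies.** Efficacy population (12-month data required) → Efficacy analysis (used for all analyses) → Biopsy results and Initiation of additional therapy (no set of their own). The safety population is assigned to safety endpoints only. The three outputs therefore use the 12-month-biopsy set.

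**2. What is lost by construction.** The month-12 window opens at 12 − 2 = month 10. A man whose prostate is removed before then cannot give an in-window biopsy and is outside the set. The curve must therefore show no prostate removal in months 0 to 10. A confidence interval does not cover this, because it is not sampling error.

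**3. What is lost only in part.** Retreated men stay on the visit schedule (protocol 6.4.10). Radiation or hormone therapy does not preclude a biopsy. Men are also excluded for major deviations, which need not relate to failure.

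**4. Inputs for size.** The protocol synopsis plans 50 treated to obtain at least 44 evaluable. The 44 reproduces by the normal approximation at the SAP's one-sided 10%: (1.2816 × √(0.70 × 0.30) + 0.8416 × √(0.836 × 0.164))² / 0.136² = 43.7, rounded up to 44. Here it serves only as the planning minimum, leaving 50 − 44 = 6 men out. All other inputs below are assumptions.

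**5. Additional therapy by month 12.** Let j be users inside the set and k users among the men left out. The SAP output is j/44; the figure for all treated men is (j + k)/50.

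| Assumption | Shown by the SAP set | All 50 treated |
|---|---|---|
| j=0, k=0 | 0/44 = 0% | 0% |
| j=0, k=1 | 0% | 1/50 = 2% |
| j=0, k=3 | 0% | 3/50 = 6% |
| j=0, k=6 | 0% | 6/50 = 12% |
| j=1, k=0 to 6 | 1/44 = 2.3% | 1/50 to 7/50 = 2% to 14% |

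The exact 95% upper limit for 0/44 is 1 − 0.025^(1/44) = 8.0%. Only k=5 (10%) and k=6 (12%) lie outside it. With j=0 and a set of 47, 0% compares with 0/50 to 3/50, or 0% to 6%. With a set of 40, it compares with 0/50 to 10/50, or 0% to 20%.

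**6. Month-3 positivity.** Assume all 50 were biopsied, 10 of the 44 were positive, and m of the 6 left out were positive. Shown: 10/44 = 22.7% (exact 95% CI 11.5% to 37.8%). All treated: (10 + m)/50 = 20%, 22%, 26%, 32% for m = 0, 1, 3, 6. Break-even is m = 6 × 10/44 = 1.36, so the rate is understated only if m is 2 or more. Every scenario lies inside the interval. Other assumed counts behave alike: 5/44 = 11.4% against 10% to 22%; 15/44 = 34.1% against 30% to 42%.

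**7. Retreated men.** The SAP does not make clear whether they belong to the main analysis or only to the secondary one. If r of the 10 positives were retreated and left out, the main figure is (10 − r)/(44 − r): r=5 gives 5/39 = 12.8%; r=10 gives 0/34 = 0%.

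**8. Conflict in the primary analysis.** SAP, Handling of missing data, counts a missing month-12 biopsy as a failure. The primary analysis section counts men with pattern 4 or 5 before month 12 and radical therapy as failures. The population rule has already excluded everyone in the first group and many in the second.

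**The case against.** The strongest reply is that the SAP evidently meant to keep these men. The missing-biopsy rule, the early-radical-therapy rule and the competing-risk analysis all presuppose them, so the fault may be one stray clause whose more serious effect is on the primary endpoint. That is a fair account of the cause. But the two failure rules are limited to the primary analysis, and the competing-risk wording does not redefine the set; a programmer following the text would drop these men.

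Second, the routes out are narrower than they may look. A positive month-3 biopsy ordinarily permits retreatment, and withdrawal after a grade 3 or 4 event has an exception through the IRB. The SAP also does not define the 12-month biopsy by the visit window. The first two points stand, which is why the loss is described as general and not universal. The IRB exception is absent from the deterioration criterion in protocol 5.5.4. On the third, the requirement to comply with protocol follow-up supports excluding out-of-window biopsies, although this remains an inference.

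Third, the numbers are modest: j=0 is assumed, most scenarios lie within the confidence intervals, and month-3 bias can run the other way. All of this stands. It limits the claim about size; it does not justify the selection.

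Finally, the protocol's intention-to-treat set is not the same as all treated men. It comprises enrolled men with entry CRFs, and enrolment happens at consent, so some may have no VTP date. This is correct, and the remedy must keep the two sets distinct.

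**Conclusion.** The point holds: the plan is wrong as written. For prostate removal before month 10, the stated population can only omit events. For other additional therapy and for month-3 positivity, understatement is likely but not guaranteed. With 50 treated and 44 in the set, the gap for early therapy is at most 12 percentage points when no user is in the set.

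The actual size cannot be known from the documents. It depends on how many men are left out, why, and whether replacement of early withdrawals (protocol 5.5.6) raises the number treated above 50. The affected results are descriptive, so this should be corrected but does not by itself alter the test of the primary endpoint. The contradiction over missing 12-month biopsies does touch the primary analysis and needs reconciling in its own right. Within the therapies the protocol lists, only its intention-to-treat display could show additional treatment, and the SAP has dropped that display without recording the change.

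**What to change.** - Name the population in SAP, Efficacy analysis, Biopsy results and Initiation of additional therapy.
- Run time to additional therapy, time to radical therapy and the cumulative-incidence analyses on all VTP-treated men, with time zero at VTP. State that start date in Initiation of additional therapy.
- Run the month-3 table on all treated men with a month-3 biopsy, whether or not later retreated, and say which analyses include retreated men.
- Keep the efficacy population as a sensitivity analysis.
- Remove the 12-month-data condition from the efficacy population, or reconcile it with the missing-biopsy rule and the early-radical-therapy rule.
- Restore the protocol's intention-to-treat display, or record its omission under changes from the planned analysis. Keep it distinct from the all-treated set, since it may contain untreated men.

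The cost is SAP wording and a little more analysis. Estimates may be less favourable. One limit remains: protocol 5.5.3 follows withdrawn men for safety, so therapy begun after withdrawal may be incompletely captured, and the report should say how many men this affects.

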8.2 Post Treatment MRI

Prostate MRI

MRI of the pelvis and prostate gland will be performed at 3 months and 12 months following VTP treatment. Additional MRI may be performed at the discretion of the investigator up to 60 months. Results from these studies are used to confirm expected treatment effects to the prostate gland as well as evaluate for any extra-prostatic tissue changes that may be associated with side effects and find any suspicious lesions within the prostate. Any suspicious volumes meeting PIRADS (version 2) criteria of level 4 or 5 found on MRI will be targeted with at least 2 cores taken from each suspicious lesion. Additional clinically actionable findings identified on MRI will be left to the discretion of the treating physician. Lymph nodes that are 15 mm in diameter or smaller in size will be considered negative by convention although may be biopsied at the discretion of the physician. Lymph nodes greater than 15 mm in diameter will be considered suspicious by convention and will require biopsy confirmation of cancer to be classified as metastases.

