Quality of life is assessed using validated questionnaires. The IPSS comprises seven questions on the urinary symptoms plus one general question about the QOL related to urinary symptoms, whereas the IIEF comprises 15 questions. For both questionnaires, patients self-rate their responses: for the IPSS, using a six-point scale where 0 indicates 'none' or 'normal', whereas 5 indicates the worst response; for the IIEF, using a five- or six-point scale where 0 indicates 'no sexual activity', and 5 indicates the best response (questions 1 to 10), or where 1 indicates the worst response and 5 the best response (questions 11 to 15).

- Rate of adverse events following treatment

As described in section 9.1, adverse events will be recorded and reported descriptively. Events will be annotated and graded according to National Cancer Institute Common Toxicity Criteria version 4.03.

- Severe prostate cancer-related events: cancer extension to T3, metastasis or prostate cancer-related death

Stage progression to T3 disease (extracapsular extension or seminal vesical invasion), metastasis or cancer-related death will be assessed based on tissue confirmation with biopsy or post-mortem evaluation. Radiographic evidence of suspicious findings will not be utilized unless confirmed with tissue sampling.

- Use of secondary cancer therapies following VTP treatment

Patients who proceed to additional therapies for prostate cancer treatment such as radiation, surgery, hormone or chemo therapies will be documented. Adjunctive surgical or medical therapies that are not intended as cancer treatments but for management of post-treatment related events will be recorded under adverse event reporting and graded appropriately.

- Serum PSA measurements in ng/mL.

Patients blood will be drawn and PSA level determined at 1, 3, 6, 12 months and annually thereafter. Changes from baseline will be determined.

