### ***Study design***

#### **Assessments and study duration**

This is a single center, single-arm, open-label, 60-month follow-up phase IIb clinical trial with assessments at 3, 12, 24, 36, 48 and 60 months.

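### Among men with a protocol deviation, the PI decides which deviations are major with early outcome data available, so exclusion from the primary analysis can depend on early outcome

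*SAP*

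**What the plan says.** The SAP (Efficacy population) admits men who met the eligibility criteria, complied with follow-up, and received the intended drug dose, LDI and light energy. They must also have "had no major protocol deviations and provided data at the 12 month biopsy". A major deviation is "defined as one which, in the opinion of the PI, could importantly influence the result of the 12 months biopsy" and one "which is adjudicated before the 12-month biopsy". The SAP gives no list of such deviations, no independent or blinded adjudicator, and no earlier cut-off.

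This set carries the whole efficacy analysis: "All analyses will include the “efficacy population” as described above". The SAP defines no all-treated efficacy set. Protocol 10.2.2.4 has an intention-to-treat population but ties only descriptive statistics to it.

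The SAP describes a "single center, single-arm, open-label, 60-month follow-up phase IIb clinical trial". Before adjudication closes, the protocol schedules several outcome measures:

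- Biopsy (7.1): "All subjects will undergo biopsy at 3 and 12 months according to protocol".
- MRI (8.2): "MRI of the pelvis and prostate gland will be performed at 3 months and 12 months following VTP treatment".
- PSA (10.4.1): "Patients blood will be drawn and PSA level determined at 1, 3, 6, 12 months and annually thereafter".

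**The concern.** In a single-arm trial the primary result is one proportion compared with 70%, so a decision about who is in the denominator moves the result directly. Requiring adjudication before the Month 12 biopsy keeps the Month 12 histology out of that decision. It does not keep out the Month 3 histology, the imaging or the PSA course. The test for a major deviation is whether it could affect the Month 12 result, and the person applying it can see how the man is doing. Two men with the same deviation could be handled differently according to their Month 3 findings, and nothing in the SAP would prevent or reveal it.

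The treatment-related grounds for exclusion (eligibility, dose, LDI, energy) are already separate conditions in the same definition, and for the first treatment they are known by the day of VTP. The opinion clause therefore mainly reaches other, often later, deviations, where early outcome is visible.

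**Working it through.** **What can be known, and when.** The Month 6 visit has a window of ±2 months, so it falls no later than Month 8. The Month 12 visit has the same window, so its biopsy falls no earlier than Month 10. On schedule, PSA at Months 1, 3 and 6 and the Month 3 biopsy and MRI therefore all precede the deadline. Month 12 PSA and MRI may do so too, because PIRADS 4 or 5 lesions on MRI are targeted at biopsy (Protocol 7.1).

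**Inputs.** Null rate 0.70, assumed rate 0.836, one-sided alpha 10%, power 80%, N = 44 (SAP, Planned sample size). Success requires a one-sided 90% lower bound, rounded to 0.01, of at least 70%, stated as 35 of 44 (SAP, Primary efficacy analysis). Fifty men are treated to obtain at least 44 evaluable (Protocol synopsis).

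**The plan's own figures.** N = [(1.2816·√(0.70·0.30) + 0.8416·√(0.836·0.164)) / 0.136]² = 43.7, so 44. The Clopper-Pearson lower bound is L(r, n) = the 10% quantile of Beta(r, n − r + 1). L(35, 44) = 0.6964, which rounds to 0.70 and passes. L(34, 44) = 0.672 fails. Both stated figures reproduce. With X ~ Bin(44, p), P(X ≥ 35) is 10.9% at p = 0.70 and 82.6% at p = 0.836.

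**Effect of removing failures.** If k failures are removed from N men, the responders stay and the set shrinks to N − k. Let c(n) be the smallest r that passes the SAP rule at size n. Then

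P(false success) = P(X ≥ c(N − k)), X ~ Bin(N, 0.70).

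The value of k is an assumption, since the documents give no deviation rate.

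| Start | Failures removed | Passing count | False success |
|---|---|---|---|
| 44 | 0 | 35/44 | 10.9% |
| 44 | 1 | 35/43 | 10.9% |
| 44 | 2 | 34/42 | 18.9% |
| 44 | 3 | 33/41 | 29.4% |
| 50 | 0 | 40/50 | 7.9% |
| 50 | 3 | 38/47 | 22.3% |
| 50 | 5 | 36/45 | 44.7% |

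As an example, 33/44 (75.0%) misses the required 35. With three failures removed, 33/41 (80.5%) has lower bound 0.702 and passes.

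**A graded version.** Suppose each failure among 44 is removed with probability d and no responder is removed. The apparent rate is 0.70 / (0.70 + 0.30·(1 − d)).

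| d | Apparent rate | False success |
|---|---|---|
| 10% | 72.2% | 14.3% |
| 20% | 74.5% | 23.0% |
| 30% | 76.9% | 34.7% |

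**Neutral comparison.** If three exclusions were unrelated to outcome, the expected number of failures among them would be 3 × 0.30 = 0.9. The chance that all three are failures would be 0.3³ = 2.7%; for five it is 0.3⁵ = 0.24%.

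**The case against.** A reader might infer that the PI can drop any man who looks likely to fail, or that the whole efficacy population rests on opinion. The documents support neither. A man must have an actual protocol deviation, and opinion governs only the major-deviation clause. The eligibility, dose, LDI and energy conditions stand on their own.

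Nor is the timing limit the only protection:

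- The SAP's primary efficacy analysis counts pattern 4 or 5 found before 12 months and followed by radical therapy as failure.
- Its missing-data section counts a missing Month 12 biopsy as failure.
- The protocol requires descriptive statistics on an intention-to-treat set regardless of deviations.

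The documents give no figure for how well MRI or PSA predicts the Month 12 biopsy. The removal counts are assumed, and taking only failures is extreme, as the neutral comparison shows. Early adjudication is also permitted.

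All of this narrows the point. It does not close it. The radical-therapy rule misses a man with poor Month 3 findings, no radical therapy, and a deviation called major. The missing-biopsy rule conflicts with the efficacy population definition, which requires Month 12 biopsy data, so as written it may never operate. The descriptive intention-to-treat summary carries no test and is absent from the SAP. Early adjudication is possible but not required. Protocol 5.5.4 uses a different, safety-based meaning of major violation and so does not constrain the SAP's definition.

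**Conclusion.** The point stands in a limited form. For men who have a protocol deviation, the SAP lets exclusion from the primary analysis be decided by opinion while early outcome data are available. Its existing failure rules cover only some of these men, and no all-treated efficacy analysis would show the effect.

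The figures measure sensitivity. They assume a true rate of 70%, the SAP's rule reapplied at the reduced size, exclusions confined to failures, and a number of exclusions that the documents do not supply. It would be wrong to read 29.4% or 44.7% as the trial's expected error rate, or to conclude that selective exclusion is intended or likely; the text only permits it. What the figures do show is that two or three discretionary exclusions can decide a trial of this size. The change is worth making because it costs little.

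**What to change.** In the SAP's efficacy population definition:

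1. Replace the PI's opinion with a fixed list: eligibility breach, or drug dose, LDI or energy outside protocol at the first treatment. Adjudicate it from the eligibility record and the VTP report form before the Month 3 biopsy result is available.
2. List deviations at re-treatment or later, but do not let them exclude a man from the primary analysis. Re-treatment follows the Month 3 biopsy, so its deviations cannot be judged without that result.
3. Remove follow-up compliance and having Month 12 biopsy data as conditions of entry, so that the rule counting a missing biopsy as failure can operate.
4. State that a man given any other prostate cancer therapy before the Month 12 biopsy is not counted as a responder. The present rule reaches only radical therapy after early pattern 4 or 5, so without this step item 2 could let a man given, for example, hormonal therapy count as a success.
5. Report an all-treated analysis, with missing counted as failure, alongside the primary one.

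The cost is SAP wording, with no new data or staff. A few men with later deviations stay in, and the reported rate may be slightly lower. If all 50 treated men have a Month 12 result, the SAP's rule needs 40/50, with a false-success chance of 7.9% at 70% and power of 81.3% at 83.6%. Missing biopsies counted as failures would lower that power.
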